## 2.8 Results of a single-center, double-blinded, RCT of arginine therapy for children with VOE

A total of 56 children  $> 3$  years old admitted to for VOE were enrolled in this NIH-supported arginine trial (*NHLBI K23 award HL-04386-05*). Mean age was  $13.9 \pm 4$  years (range 3.6–19 years), and 52% were female; 73% had Hb-SS, 18% Hb-SC and 9% carried S- $\beta$  thalassemia. Patients received IV arginine (100mg/kg TID) or placebo during hospitalization. **RESULTS:** Patient characteristics were similar between treatment and placebo groups. Mean time between ED triage and delivery of first randomized study drug dose was  $20.4 \pm 11$  hours, with no difference between the placebo and treatment arm. A significant reduction in opioid use (defined as total opioid use in morphine equivalents during hospitalization in mg/kg) by 54% was observed in the arginine treatment arm compared to placebo (mean  $\pm$  SEM:  $1.9 \pm 0.4$  mg/kg vs.  $4.1 \pm 0.8$  mg/kg;  $p=0.02$ ; Fig 4 A). Pain scores were similar at presentation, but significantly lower at discharge in the arginine arm vs. placebo (Fig 4 B). A clinically relevant trend of decreased hospital length of stay (LOS) by 17 hours favored patients treated with arginine. Total IV opioid use (mg/kg) correlated strongly to LOS ( $r=0.86$ ,  $p < 0.0001$ ), and represents a surrogate biomarker of LOS to evaluate study drug efficacy (Fig 4 C). Rates of ACS, transfusion and AEs were similar in both arms. No drug-related AEs were observed. No significant differences were observed between pre and post therapy liver or renal function, or hematological parameters in the arginine group vs. placebo.

[figure not shown]

Figure 4: Impact of arginine therapy on total opioid use, pain scores, & LOS. **A.** Arginine supplementation (unfilled circles) led to a significant & clinically relevant reduction in total opioid use by 54% over the course of the hospital stay compared to the placebo group (filled circles). The difference remains significant even when the 2 outliers with the largest total opioid use in the placebo arm are excluded from the analysis ( $p=0.04$ ). **B.** Pain scores were significantly lower at discharge in the arginine group compared to placebo by 2 cm. **C.** Correlation between Total Opioid Use (mg/kg) and Length of Hospital Stay (Days).

[figure not shown]

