### **Secondary Outcome Measures:**

- 1) Total parenteral opioid use (morphine equivalents, mg/kg)
  - Data being collected: time of IV placement, opioid monitoring
- 2) Pain scores at presentation vs. discharge; Daily highest and lowest pain scores recorded
  - Data being collected: Pain Scores (0–10 scale)
- 3) Three Patient Reported Outcomes (PROs),  performed within 12 hours of study drug delivery and on the day of discharge.
  - (a) PROMIS Pain Interference
  - (b) PROMIS Pain Behavior
  - (c) PROMIS Fatigue

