- c – Research labs: will be obtained with routine daily blood draws whenever possible and may be drawn on days when the research and clinical team suspect the patient may be discharged to avoid multiple venipunctures. In the event the patient is not discharged on that date, discharge labs should be drawn again prior to discharge. Baseline labs to be drawn before the start of study drug.
- d – Screening CMP from a clinically ordered CMP or the last CMP in the medical record within the last 12 months will be reviewed. If there are any values within higher than protocol defined cut offs for study drug withdrawal, then a CMP is to be drawn and reviewed prior to randomization. For participants with normal past CMP, a CMP will be done on day 2.
- e – Pregnancy test obtained at Pre-Dose for females 13 years and older.
- f – The first set of Vital Signs (including oxygen saturation) and Pain scores will be captured when the patient first presents to the Emergency Department. The highest and lowest pain scores will be recorded from Day 1 through Day 8 (or within 6 hours of Discharge). The first set of vitals signs after 6 am will be collected up until Day 8/Discharge, whichever comes first. Ensure oxygen saturation is captured at Pre-Dose and within 6 hours of Discharge.
- g – Symptoms Questionnaire will be completed daily through Day 14 or Discharge.
- h – Use of Parenteral Opioids will be documented every shift by nursing staff per standard protocol, including opioids delivered by the PCA device as well as any intravenous, intranasal and/or oral opioids used. Data on daily opioid use will be collected and recorded.
- i – AEs and SAEs will be monitored daily through discharge or through 14 days of hospitalization; Return ED visits and hospitalizations will be followed for 28 days after hospital discharge.
- j – Patients will be randomized within 12 hours of their initial dose of parenteral opioid in the ED or ward and Arginine will be administered TID.

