## 5.1 Specific Aim Analyses

**Specific Aim 1: To determine the efficacy of IV L-arginine, when added to standard therapy, on the time-to-crisis resolution in children with SCD and VOE compared to placebo.**

The primary outcome (time-to-crisis resolution) will be analyzed by a Van Elteren test, stratified by clinical center and age group. The significance level for the primary comparison will be set at 0.05. The total length of stay in the hospital will also be analyzed, and this is expected to show the same result as the analysis of the primary outcome.

In addition to the assessment of the statistical significance of the treatment effect, the distribution of the primary outcome in each treatment arm using standard summary measures and an estimated difference in means between the two arms with a two-sided 95% confidence interval will be described.

The overall significance level for statistical tests on the secondary outcomes will be set at 0.05. Holms method will be used to adjust for multiple comparisons. The numeric secondary outcomes (opioid use, change in pain, and PRO measures) will be analyzed in the same manner as the primary outcome.

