## 5.3 Subgroups

The formal subgroups specified for this trial will be age group, hydroxyurea use, and sex. The interaction between assigned treatment and each subgroup factor in a linear model, at a significance level of 0.05/3 will also be tested. The model will include a main effect for treatment, a main effect for subgroup factor, and an interaction between the subgroup factor and treatment. Secondary outcomes in similar models will also be observed.

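### Change in pain is tested without adjusting for the presentation score already collected: the test is valid, but it can lose power when presentation and discharge pain are weakly to moderately correlated

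*Combined protocol and SAP*

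**What the plan says.** Section 5.1 sets the primary method: "The primary outcome (time-to-crisis resolution) will be analyzed by a Van Elteren test, stratified by clinical center and age group". For the primary outcome it adds that "an estimated difference in means between the two arms with a two-sided 95% confidence interval will be described". It then carries the approach over: "The numeric secondary outcomes (opioid use, change in pain, and PRO measures) will be analyzed in the same manner as the primary outcome". Secondary tests share an overall level of 0.05 under Holm's method.

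Section 4.5 lists the pain outcome as "Pain scores at presentation vs. discharge; Daily highest and lowest pain scores recorded", on a 0–10 scale. Note f to the Schedule of Events says that the first vital signs and "Pain scores will be captured when the patient first presents to the Emergency Department", which is before study drug.

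The only linear model in the plan is the subgroup model of Section 5.3, which is also to be applied to secondary outcomes: "The model will include a main effect for treatment, a main effect for subgroup factor, and an interaction between the subgroup factor and treatment". It has no term for presentation pain.

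Section 5.2 sizes the trial on the primary outcome alone. The documents state no power, SD or presentation–discharge correlation for pain.

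**The concern.** A change score subtracts the whole presentation score, so it fixes the weight on that score at 1. Adjustment estimates the weight from the data. If presentation pain predicts discharge pain only weakly, subtracting all of it adds noise to the comparison.

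Hypothesis 3, that arginine improves pain scores, rests on this test. At stake are its power and the width of any confidence interval reported with it. Type I error, the primary analysis and the sample size are not at stake.

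**Working it through.** **The plan's own figure.** There is none for pain. For the primary outcome, the inflation step reproduces: 166 × 1.08 = 179.3, stated as 180 per arm. The 166 was simulated from another trial's data, which the documents do not contain, so it cannot be reproduced. Nothing below depends on it.

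**Inputs from the documents.** 180 per arm, 1:1 allocation, two-sided tests, integer scores from 0 to 10, and 10 sites × 2 age groups = 20 strata, or 360/20 = 18 patients per stratum on average. The earlier trial in Section 2.8 gives the only pain effect: "Pain scores were significantly lower at discharge in the arginine group compared to placebo by 2 cm". I take 2 cm as 2 points on the 0–10 scale (assumption).

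**Assumed inputs.** The SDs of the presentation score (s1) and discharge score (s2), their correlation r, latent means of 7.5 and 4.5, and an effect of 1 point.

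**Step 1: linear theory.** The variance of the change-score comparison relative to the adjusted one is

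(s1² + s2² − 2·r·s1·s2) / (s2²(1 − r²)) = 1 + (k − r)²/(1 − r²), with k = s1/s2.

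This is never below 1 and equals 1 only at r = k. With equal SDs it reduces to 2/(1 + r).

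| s1/s2 | r = 0.2 | r = 0.4 | r = 0.6 |
|---|---|---|---|
| 2.5/2.5 | 2/1.2 = 1.67 | 2/1.4 = 1.43 | 2/1.6 = 1.25 |
| 2/2.5 | 1 + 0.36/0.96 = 1.38 | 1 + 0.16/0.84 = 1.19 | 1 + 0.04/0.64 = 1.06 |
| 1.5/2.5 | 1 + 0.16/0.96 = 1.17 | 1 + 0.04/0.84 = 1.05 | 1.00 |
| 2.5/2 | 1 + 1.1025/0.96 = 2.15 | 1 + 0.7225/0.84 = 1.86 | 1 + 0.4225/0.64 = 1.66 |

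These ratios are for a linear analysis of unrounded scores. The planned test is a rank test, so it was simulated.

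**Step 2: the rank tests.** 4,000 trials per cell, bivariate normal scores rounded and truncated to 0–10, 20 strata of 18. Power at alpha 0.05, Van Elteren on change vs stratified rank ANCOVA:

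| s1/s2 | r = 0.2 | r = 0.4 | r = 0.6 |
|---|---|---|---|
| 2.5/2.5 | 83 vs 95% | 92 vs 97% | 98 vs 99% |
| 2/2.5 | 89 vs 95% | 94 vs 97% | 99 vs 99% |
| 1.5/2.5 | 92 vs 95% | 96 vs 97% | 99 vs 99% |
| 2.5/2 | 92 vs >99% | 97 vs >99% | >99 vs >99% |

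The squared ratio of mean z statistics gives the extra patients the change score would need. In the same row order this is 53/31/14%, 32/16/1%, 17/3/−4% and 83/57/34%. A negative value favors the change score. At SDs 2/2.5 and r = 0.8 it is −7%, with power about 100% for both.

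The SDs and r above are latent. After rounding and truncation the observed SDs are 2.19/2.41, 1.85/2.41, 1.47/2.41 and 2.19/2.00, and the observed r is 0.19/0.38/0.57.

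**Step 3: validity.** Null rejection at 0.05 was 0.042–0.057 for the change score and 0.045–0.054 for rank ANCOVA (Monte Carlo SE 0.003).

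**Step 4: interval width.** Simulated 95% CI half-widths in points for the difference in means, change vs linear ANCOVA, at r = 0.2/0.4/0.6:

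- Equal SDs: 0.60 vs 0.48, 0.53 vs 0.46, 0.44 vs 0.41.
- SDs 2/2.5: 0.56 vs 0.48, 0.50 vs 0.46, 0.42 vs 0.40.
- SDs 1.5/2.5: 0.53 vs 0.48, 0.47 vs 0.46, 0.40 vs 0.40.

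**Step 5: sensitivity.**

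- Effect of 2 points: at least 99.9% power for both analyses.
- Effect of 0.75 points, equal SDs of 2.5 (800 runs per setting, Van Elteren on change vs on discharge pain residualized on presentation pain): 56 vs 75% at r = 0.1, 65 vs 79% at 0.3, 77 vs 86% at 0.5, 93 vs 94% at 0.7.
- Alpha 0.01, the first Holm step if the family is opioid use, pain and three PROs (0.05/5, assumption), 1-point effect, equal SDs, r = 0.2: 62–66% vs 84–85% across repeat simulations.
- Unequal strata of 8 to 32 patients, equal SDs: 84 vs 95%, 93 vs 97%, 98 vs 99% at r = 0.2/0.4/0.6.

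**The case against.** The plan contains no error here. It applies one valid, prespecified method to every numeric outcome, and a different method for pain is a preference about efficiency. At the only pain effect in the documents, 2 points, nothing is lost. In the equal-SD case at r = 0.2 the mean z is about 2.9 at 1 point. At 1.5 points it is about 4.35, and the change score then has roughly 99% power. The loss therefore needs a smaller effect, which the documents do not supply.

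The correlation, the SDs and the latent means are also assumed, and across the grid the sign is not fixed: 83% more patients at one end, 7% fewer at the other. In five of the twelve power cells the gain rounds to 1 percentage point or less. Eligibility requires parenteral opioids and excludes patients who respond well enough to two IV doses. This may compress presentation scores near the top of the scale and favors the small-loss rows. The 2.5/2 row has no support in the documents. Finally, the difference in means with its interval is written for the primary outcome, and its use for pain is inferred from the same-manner sentence.

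All of this stands, and it limits the point to an optional improvement. It does not remove it. A 2-point difference from a small single-center trial may be optimistic, the plan does not show that r is high, and applying Holm widens the gap at low r.

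**Conclusion.** The concern holds as an efficiency point on one secondary outcome, graded as something to consider. No part of the plan adjusts pain for the presentation score.

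If the true effect is near 1 point, r is 0.2–0.4 and presentation scores vary no more than discharge scores, the change score gives up about 1 to 12 percentage points of power at alpha 0.05. The loss is largest with equal SDs and low r. It is close to nil when presentation scores are clearly less variable and r is moderate, and at a 2-point effect. Where discharge scores are more variable and r is high, the change score can be about 4–7% more efficient, with nearly equal power.

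Confidence is medium, because r, the SDs and the effect size are all assumed.

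**What to change.** For pain only, prespecify before unblinding a rank ANCOVA of the discharge score on the presentation score, stratified by center and age group. State whether the slope is pooled or fitted within strata; with about 18 patients per stratum, a pooled slope is steadier.

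Report the baseline-adjusted difference in discharge pain with a 95% CI from a linear model containing treatment, presentation pain, center and age group, in place of the unadjusted difference in mean change. Keep the Van Elteren test on change as a sensitivity analysis.

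The cost is SAP wording and slight extra programming. No patients, procedures or data elements are added. The effect becomes an adjusted discharge score instead of a raw change, which is close to how Section 2.8 reports the earlier trial: "Pain scores were similar at presentation, but significantly lower at discharge in the arginine arm vs. placebo". The only statistical price is the possible 4–7% loss of efficiency when discharge scores are clearly more variable and r is high.

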### 4.2 Randomization

Subjects will be randomized to receive either IV arginine or placebo. Permuted-blocks, stratified by clinical center and age group (<12 vs.  $\geq 12$ ), will be used. Equal allocation randomization tables will be provided by the Data Coordinating Center to the site research pharmacies. Randomization numbers will be delivered to the clinical center staff using a web-based system. This system will use each enrolled patient’s age group (<12 vs.  $\geq 12$ ) to deliver the next assigned treatment. Each site research pharmacy will use a randomization number to look up the treatment assignment and prepare the appropriate study drug. The randomization number will be recorded in the database.

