#### 4.5.1 Schedule of Events

The Schedule of Events (table 3) summarizes data collection for each time point in the study.

Table 3: Schedule of Events

	Screening	Pre-Dose 	Day 1 	Day 2 	Day 3-7 	Day 8 or Discharge 	Day 14 and/or Day 28 
I/E	X	X					
Demographics and Genotype		X					
Study Treatment Assignment		X					
Medical History	X	X					
Pain Crisis Start Date and time a		X					
Time of Last IV opioid/Pain Crisis End date and time b						X	
Number of ED visits/hospitalizations in last year (excluding current)		X					
ED admission information		X					
Time of IV placement		X					
Conmeds		X	X	X	X	X	
CMP d	X d	X d		X d			
BHCG e		X					
Research Labs		X		X		X	
Vital Signs f	X		X	X	X	X	
Pain Score f	X		X	X	X	X	
PROs (PROMIS/Peds) QL/ASCQ-Me (adults)		X (within 12 hours)					X
MQS Score		X	X	X	X	X	X
Symptoms Questionnaire g		X		X	X	X	X
Opioid Monitoring h	X	X	X	X	X	X	X
Maintenance Fluid Monitoring h		X	X	X	X	X	
AE i		X	X	X	X	X	X
SAE i		X	X	X	X	X	X
Study Drug Administration j			X	X	X	X	

Continued on next page...

Table 3 – *continued from previous page...*

---

- 1 – Predose is all information that is collected before the start of study drug.
- 2 – Day 1 is from the start of Study Drug to midnight of the day study drug is started. Pre-Dose and Day 1 may occur on the same day.
- 3 – Day 2 is the day after study drug is administered (starting at midnight of the day the study drug is started).
- 4 – Individual patient hospitalization duration will vary. Patients may be discharged at any time between Day 1 through Day 7.
- 5 – Day 8 is the day that the last dose #21 will be given for patients who have not yet been discharged.
- 6 – If patients are not discharged by Day 8, an AE/SAE review will occur daily until Day 14. ED revisits and hospital admissions will be captured through 28 days following hospital discharge.
- a – Pain Crisis start date/time is defined as the date/time the patient started experiencing pain (this could be before ED visit).
- b – Pain crisis end date/time is defined as the date/time of last dose of parenteral opioid delivery.

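### Section 5.1 leaves the PROMIS endpoint undefined (discharge score or change) and never adjusts for the pre-dose score, which costs efficiency but does not cause bias

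*Combined protocol and SAP*

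**What the plan says.** Section 4.5 lists three PROMIS scales as secondary outcomes, "performed within 12 hours of study drug delivery and on the day of discharge". In the Schedule of Events (Section 4.5.1) the first PRO mark stands in the Pre-Dose column, annotated with the same 12-hour window, and a footnote states: "Predose is all information that is collected before the start of study drug".

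For the analysis, Section 5.1 says: "The numeric secondary outcomes (opioid use, change in pain, and PRO measures) will be analyzed in the same manner as the primary outcome". The primary method is: "The primary outcome (time-to-crisis resolution) will be analyzed by a Van Elteren test, stratified by clinical center and age group". These strata match Section 4.2: "Permuted-blocks, stratified by clinical center and age group". On multiplicity, Section 5.1 says "The overall significance level for statistical tests on the secondary outcomes will be set at 0.05" and names Holm's method, but gives no family size.

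The pain score is treated differently. Section 4.5 defines it as "Pain scores at presentation vs. discharge; Daily highest and lowest pain scores recorded", and Section 5.1 attaches the word change to pain. Neither section says which PRO value is analysed. The subgroup models in Section 5.3, which also cover secondary outcomes, contain only treatment, the subgroup factor and their interaction.

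**The concern.** The primary outcome is a time from first study drug, so it has no baseline value. Copying its test to the PROs leaves no place for the one covariate likely to explain most of the spread in a discharge PRO score: the same scale completed near presentation.

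Two things are at stake. First, precision: the between-arm comparison is wider than the collected data require, in a Holm-adjusted family for which the plan states no PRO power. Second, specification: discharge score and change can differ a good deal in power, and the choice should not remain open once data are seen.

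**Working it through.** **Plan's own figures.** No power or effect size is stated for any PRO, so there is none to reproduce. The trial size rests on the primary outcome: 166 per arm, and 166 × 1.08 = 179.3, which rounds up to the stated 180. The 166 was simulated from external trial data and cannot be rebuilt from the documents.

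**Inputs from the documents.** Two-sided tests (Section 5); equal allocation (4.2); 10 sites (1.1) × 2 age groups = 20 strata, so 360/20 = 18 children per stratum on average; overall secondary level 0.05 (5.1).

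**Assumptions.** Correlation r from 0 to 0.7; an effect giving 80% power on the discharge score; complete pre-dose scores; equal variance at both assessments; normal theory. For the level, my count of opioid use, pain and three PROMIS scales gives five tests, so a first Holm step of 0.05/5 = 0.01.

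**Variance, relative to the discharge score.**
- Discharge score: 1
- Change: 2(1-r)
- Adjusted for the pre-dose score: 1-r²

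Change minus adjusted is 2(1-r) - (1-r²) = (1-r)², which is never negative. Adjustment therefore does at least as well as either endpoint at every r from 0 upward. It saves 9%, 25% and 49% of the discharge-score variance at r = 0.3, 0.5 and 0.7.

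**Power.** The noncentrality for 80% power is 1.960 + 0.842 = 2.802 at 0.05, and 2.576 + 0.842 = 3.417 at 0.01 (unrounded terms). Divide by the square root of the relative variance, subtract 1.960 or 2.576, and take the normal probability. Example at r = 0.5, adjusted, 0.05: 2.802/√0.75 = 3.235; 3.235 - 1.960 = 1.275; power 0.899.

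| r | change, 0.05 | adjusted, 0.05 | change, 0.01 | adjusted, 0.01 |
|---|---|---|---|---|
| 0 | 0.508 | 0.800 | 0.437 | 0.800 |
| 0.3 | 0.658 | 0.836 | 0.623 | 0.843 |
| 0.5 | 0.800 | 0.899 | 0.800 | 0.915 |
| 0.7 | 0.951 | 0.975 | 0.967 | 0.986 |

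The discharge score is 0.800 throughout.

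**Simulation of the stratified test itself.** 2,000 trials, 20 strata, 180 per arm, level 0.01, assumed effect 0.35 SD; the adjusted column applies Van Elteren to residuals from one pooled slope on baseline.

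| r | discharge | change | adjusted |
|---|---|---|---|
| 0.3 | 0.70 | 0.52 | 0.76 |
| 0.5 | 0.71 | 0.73 | 0.86 |
| 0.7 | 0.70 | 0.92 | 0.96 |

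With no effect, rejection rates were 0.006 to 0.0125 for all three, near the nominal 0.01.

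**Missing pre-dose forms.** If a fraction p has a usable form, missingness is unrelated to the score, and the rest are mean-imputed with an indicator, the average residual variance is p(1-r²) + (1-p) = 1 - p·r². With p = 0.6 (my assumption) this is 0.946, 0.850 and 0.706 at r = 0.3, 0.5 and 0.7. Power at 0.05 is then 0.821, 0.860 and 0.915, instead of 0.836, 0.899 and 0.975.

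**Pooled or separate slopes.** In a further simulation (3,000 trials, level 0.01, about 0.80 unadjusted power, complete baselines), a rank ANCOVA with a separate slope in each of the 20 strata gave 0.76, 0.80, 0.87 and 0.96 at r = 0, 0.3, 0.5 and 0.7. One pooled slope gave 0.83, 0.88 and 0.97 at r = 0.3, 0.5 and 0.7. About 20 slopes fitted to 18 children each use up part of the gain, and cost power outright when r is near zero.

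**The case against.** A reader might infer that the plan throws the first PRO score away. The documents do not support that. The punctuation in Section 5.1 attaches change to pain, but the PRO endpoint is otherwise undefined, and Section 4.5 describes two PRO time points much as it does for pain. A change score is a plausible reading and would use the first assessment. At r = 0.7 adjustment then adds little (0.92 to 0.96 in the simulation). This limits how much is lost; it does not make the unadjusted analysis preferable, because adjustment is no worse under either reading.

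A reader might also infer bias or an inflated error rate. Neither follows: the stratified test respects the randomization strata and held its level.

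Other limits stand:
- A pre-dose form is not guaranteed. The 12-hour window in Section 4.5 could admit a form completed after the first dose, despite the Pre-Dose column.
- The PRO sample is below 180 per arm by an unstated amount, because Section 4.5 gives PROMIS no respondent at ages 3 and 4. The power figures above should not be tied to 180.
- At ages 5 to 7 only the parent completes PROMIS, and the fatigue form has 10 items for children and 8 for adults. The plan does not say which reporter's score is analysed.
- The five-test family is my count. Section 4.5 also lists daily highest and lowest pain scores, so the family could be larger.

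**Conclusion.** The point holds as a gap in specification and efficiency for the three PROMIS outcomes; it does not touch the primary outcome or the validity of the planned test. Whichever PRO value is meant, adjusting for the pre-dose score is at least as efficient. Relative to the discharge score the gain in power at 0.05 is nil at r = 0, about 4 points at 0.3, 10 at 0.5 and 17 at 0.7, and a little larger at 0.01 for r = 0.3 and 0.5. Relative to change it is largest when r is low. These figures rest on an unknown correlation, on normal theory and on complete pre-dose scores; missing forms reduce them. It is a worthwhile improvement, not a necessary correction.

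**What to change.** In Section 5.1, replace the cross-reference to the primary method, for the PROs only, with the following:
1. The endpoint for each PROMIS scale is the follow-up score.
2. It is analysed by ANCOVA on the pre-dose score from the same reporter and form, with center and age-group strata. If a rank method is preferred, use a stratified rank ANCOVA with one pooled slope, not a slope per stratum.
3. Only forms completed before the first study-drug dose count as baseline. A later form could already reflect treatment.
4. A missing baseline is mean-imputed with a missing indicator. Whether a form was completed before dosing cannot depend on the blinded arm, so this introduces no bias.
5. The reporter used at each age and the number of tests in the Holm family are stated.

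The change should be made before any unblinded PRO data are seen. It needs no new assessments, provided the completion time of the first form is recorded. The statistical cost is one degree of freedom per outcome for the slope and one more if the indicator is used. If the correlation is low there is little or no gain.
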